 - 2 categories down, eg, from ‘1. Not hospitalized’ to ‘3. Non-ICU hospitalization, requiring supplemental oxygen’
- To reflect missingness patterns as a result of study discontinuation due to a dissatisfying treatment effect or safety issues in the pimodivir treatment group, the following shifts will be applied in the pimodivir treatment group only:
 - 1 category down, eg, from ‘1. Not hospitalized’ to ‘2. Non-ICU hospitalization, not requiring supplemental oxygen’
 - 2 categories down, eg, from ‘1. Not hospitalized’ to ‘3. Non-ICU hospitalization, requiring supplemental oxygen’

In all cases, '6. Death' will be the worst hospital recovery scale category after imputation and structural shift.

Secondary Endpoints

Time from start of study drug to hospital discharge will be analyzed by a stratified Gehan-Wilcoxon test (using the stratification factors, ie, type of baseline SOC, time of onset of symptoms and baseline NEWS2). Kaplan-Meier curves, overall and by stratum, and a stratified log-rank test for time to symptom resolution will also be provided. Additionally, the data will be analyzed using an accelerated failure time model. Also, a Cox proportional hazards model will be applied. Both models will be adjusted for stratification factors. Time from ICU admission to ICU discharge and time from start to end of mechanical ventilation will be analyzed analogously to that of time from start of study drug to hospital discharge. Time from start of study drug to hospital discharge and time from ICU admission to ICU discharge will also be derived based on investigator's evaluation of the subjects' clinical status and analyzed analogously.

Total length of hospitalization, total time in ICU, and total time on mechanical ventilation will be analyzed by the stratified Wilcoxon Rank-Sum test and using the stratification factors. Corresponding 95% CIs will be derived using the Hodges-Lehman approach.

Time to return to daily activities will be assessed once daily by means of the question 'Over the past 24 hours, how much has influenza (flu) interfered with your ability to carry out your daily activities?' The responses will be dichotomized: 'Not at all' and 'A little bit' will be considered as returned to daily activities and 'Somewhat', 'Quite a Bit' and 'Very much' will be considered as not having returned to daily activities. The time to return to daily activities will be analyzed analogously to that of time from start of study drug to hospital discharge.

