5.3. Major Secondary Endpoints

5.3.1. Definition

Formulae to be used for derived variables, including data conversions, are provided in the tables below.

Note that for time-to event variables the actual date or times that the endpoint is met will be used. For the time-to-event variables, in case of death prior to the event, the subject will be censored using a time-to equal to the maximum time across all subjects.

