5.3.1.1. Clinical Outcome

Measurement	Formula
Time to hospital discharge (hours) [Time-to event]	
The time from first study drug intake to first hospital discharge (=event) in hours. Note this excludes time in hospital because of re-hospitalization (a new hospitalization is considered as a re-hospitalization if there is at least 1 day in between the start date of the new hospitalization and the end date of the previous hospitalization) and hospitalizations that ended before first intake.
 
Subjects who complete or withdraw from the study while still hospitalized will be censored at the date of completion or withdrawal. If the time is not available they will be censored at 23:59.
 
If time of end of hospitalization is not known but we have a date of discharge then time will be imputed at 23:59.
 
(Date and time of event or censoring-- date and time of first dose of study drug)/3600, rounded to one decimal.

Time to readiness for hospital discharge (days) [Time-to event]	
The time from first study drug intake until the time to readiness for hospital discharge (= event) in days, with readiness for hospital discharge defined by the investigator. In case at the date of discharge the subject is not ready to be discharged as per investigator assessment, the discharge readiness day will be set to the next day.
 
Censoring of the time will be done analogous to “Time to hospital discharge”, only using the date information, as time is not available for the event.

Total length of hospital stay (hours) [Duration]	
The total number of hours a subject stayed in the hospital during the period from first study drug intake until study termination, calculated as sum of [(end date and time of hospitalization-- start date and time of first intake)/3600], rounded to one decimal for all separate hospital stays per subject. If the time is not available it will be put at 23:59
 
If hospitalization started before first study drug intake, then datetime of first study drug will be used.
 
If hospitalization is still ongoing at study end, the end date and time will be imputed by the end date and time of the last phase as defined in table 1.

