Total time in intensive care unit (ICU) stay (hours) [Duration]	
The total number of hours a subject stayed in ICU during the period from first intake until study termination, calculated as sum of [(end date and time of discharge-- start date and time of admission)/3600], rounded to one decimal for all separate events per subject
 
In case ICU admission took place before first intake or in case the start datetime of ICU is missing, then the date and time of first intake will be used.
 
In case the ICU stay ended after the end of the trial or in case the end datetime of ICU stay is missing, then the end datetime of last contact date will be used.
 
If time of the start of ICU admission is missing then use 00:00. If time of the end of ICU admission is missing then use 23:59. The derivation of total time in ICU is analogous to “total length of hospital stay”.

Type of supplemental oxygen administration	
Tabulation will be done as collected per CRF page “Oxygen Supplementation”. In addition, the following categorization will be done:
 
 - Invasive Mechanical Ventilation - Non-Invasive Mechanical Ventilation - Non-Invasive, Non-mechanical Ventilation - None
Mechanical ventilation during study	
Incidence of mechanical ventilation (invasive or non-invasive) Categories:
 
 - Mechanical ventilation at baseline - First administration of mechanical ventilation post-baseline - No administration of mechanical ventilation
Mechanical ventilation started post-baseline	
Incidence of post-baseline mechanical ventilation (invasive or non-invasive)
 
 - Started post-baseline - Not started post-baseline 
Note: In case mechanical ventilation is present at baseline and a second episode of mechanical ventilation is initiated post-baseline, this subject will be counted as started post-baseline.

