5.3.2.1. Clinical outcome

Time-to event parameters for clinical outcome

The time-to event parameters for clinical outcome will be analyzed as described above using a stratified Gehan-Wilcoxon test, a stratified log-rank test, a Kaplan-Meier analysis, an accelerated failure time model and a Cox proportional hazards model. The Gehan-Wilcoxon test is the primary analysis for time-to-event parameters. The Kaplan-Meier analysis will provide the primary estimation of time-to-event.

Duration parameters

Descriptive statistics of the duration parameters will be shown for all subjects that had the specific event. e.g. only subjects admitted to ICU will be included in the total time in ICU analysis.

Total length of hospitalization, total time in ICU, total duration of antibiotics, and total time on mechanical ventilation will be analyzed by using the Hodges-Lehman approach. Corresponding 95% CIs will be presented as well.

Incidence parameters

For each parameter the number and percentage of subjects in each category and subcategory will be tabulated and listed. All Subjects in the applicable analysis set will be counted for the denominator of the proportion.

The occurrence (yes/no) as described for the incidence parameters will be analyzed using logistic regression as described above (Section 5.3.2).

The occurrence (yes/no) of influenza complications will be analyzed using logistic regression as described above for the following categories:

- the overall influenza complications
- the pulmonary complications,
- the extrapulmonary complications
- the infectious complications
- the non-infectious complications
- the major complications
- the minor complications
- the pulmonary complications including sinusitis and otitis

Hospital recovery scale outcome and fundamental hospital recovery scale outcome on Day 2 to 14

This parameter will be analyzed analogous to the primary endpoint: hospital recovery scale outcome on Day 6, but then for Day 2 to 14 with Day 6 excluded for the HRS and including Day 6 for the fundamental HRS. The proportional odds model will be applied, and the proportional odds assumption will be tested for the treatment effect. The same 5 dichotomization of the HRS will be analyzed using a logistic regression model. Also, similarly as the primary endpoint the Van Elteren test will be provided in case the proportional odds assumption is not valid. The MI analysis will not be applied.

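### The total-duration endpoints have no death rule, so early deaths count as short durations and can distort, or reverse, the estimated shift, chiefly for ICU and ventilation time

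*SAP*

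**What the plan says.** Protocol section 2.1.2 pairs each of three time-to-event endpoints with a total: time to hospital discharge with total stay, ICU admission to discharge with total ICU time, and start to end of ventilation with total ventilation time. Duration of antibiotic treatment is a further duration endpoint.

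SAP section 5.3.1 deals with death for the first kind only: "For the time-to-event variables, in case of death prior to the event, the subject will be censored" at the largest time seen in any subject. That places a death behind every observed event.

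SAP section 5.3.1.1 defines the totals as accumulated hours. For the ICU it reads "The total number of hours a subject stayed in ICU during the period from first intake until study termination". For hospital stay it adds "If hospitalization is still ongoing at study end, the end date and time will be imputed by the end date and time", meaning those at which the subject's last phase ends. An ICU or ventilation period that is open or has no end time is closed at last contact, and antibiotic duration has a similar rule. None of the four definitions mentions death.

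SAP section 5.3.2.1 compares the totals between arms with a Hodges-Lehmann estimate and 95% CI. Its sentence names hospital stay first and then reads "total time in ICU, total duration of antibiotics, and total time on mechanical ventilation will be analyzed by using the Hodges-Lehman approach". Descriptive statistics are limited to subjects who had the event; the SAP's example is that "only subjects admitted to ICU will be included in the total time in ICU analysis". Protocol section 11.4 says instead that the hospital, ICU and ventilation totals "will be analyzed by the stratified Wilcoxon Rank-Sum test and using the stratification factors", with Hodges-Lehmann intervals. It treats antibiotic duration in the same way.

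**The concern.** Protocol section 10.3 makes death an automatic withdrawal, and SAP section 2.1.1 ends a subject's last phase on the day of trial termination, or of last contact if later. In effect a hospital, ICU or ventilation period that is open at death closes then, and its length is analysed as if the subject had recovered. A subject who dies on Day 2 while ventilated ranks ahead of a survivor weaned on Day 10. A subject who withdraws while in hospital is censored in the time-to-event version but counted here as having a complete, short stay.

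The same death is therefore placed worst in time to end of ventilation and near best in total time on ventilation, two halves of one endpoint pair. If mortality differs between arms, the shift mixes an effect on duration with an effect on survival that can pull the opposite way.

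**Working it through.** **1. The plan's own figure.** SAP section 1.4 assumes a Day 6 placebo distribution of 30/30/25/5/5/5%, about a 38% reduction in the odds (OR 0.62), 90% power and two-sided 5%. The Whitehead formula is

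N = 12(1.960 + 1.282)² / [ln(0.62)² × (1 − Σp̄³)].

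With Σp̄³ = 0.0825 this gives N = 601.4, which reproduces the planned 600. The same OR turns 5% placebo mortality into odds of 0.05/0.95 × 0.62 = 0.0326, that is 3.16% on pimodivir.

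**2. Effect on the shift.** The documents give no durations, death times or mortality within the ICU and ventilated subsets, so these are assumptions:

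- Survivor durations are lognormal (sigma 0.7), capped at 28 days and equal in both arms, with medians of 6 days (hospital), 8 days (ICU) and 10 days (ventilation).
- Deaths are spread evenly over the window shown.
- Mortality, placebo vs pimodivir, is 5.0% vs 3.16% (hospital), 33% vs 17% (ICU) and 50% vs 25% (ventilation). The placebo values for the subsets match 5/15 and 5/10 in the planning distribution. The halving is assumed.

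The shift is the median of all pairwise differences, pimodivir minus placebo, in hours. Positive means apparent harm in the arm with fewer deaths.

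| Deaths fall on | Hospital stay | ICU time | Ventilation time |
|---|---|---|---|
| Days 1–6 | +1.5 | +21.0 | +39.0 |
| Days 1–14 | −0.2 | +4.9 | +18.7 |
| Days 1–28 | −1.5 | −14.3 | −14.0 |
| Days 7–28 | −2.4 | −28.1 | −35.5 |
| Any window, deaths set to 28 days | −2.6 | −33.3 | −42.6 |

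If pimodivir also shortens survivor durations by 10%, the Days 1–6 row becomes −10.5, +9.2 and +27.7 h.

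**3. Finite samples.** In 1,000 simulated trials with deaths on Days 1–6:

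- Hospital stay (300 per arm): shift positive in 60%, nominally significant harm in 4%.
- ICU time (45 per arm): 84% and 17%.
- Ventilation time (30 per arm): 92% and 29%.
- ICU time with equal mortality (33% in both arms): 49% positive and 2% significant harm, as expected by chance.

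**4. Dependence on death timing.** With ventilation mortality of 45% vs 25%, 30 per arm and a median survivor duration of 10 days, moving only the median day of death gives +1.1 days (Day 5), +0.3 (Day 8), 0.0 (Day 10), −0.35 (Day 12) and −0.6 (Day 14).

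**5. Dependence on the mortality gap.** Under the planning OR, the share dead among the three worst Day 6 categories barely moves: 5/15 = 33.3% on placebo and 3.16/9.86 = 32.0% on pimodivir, because the whole severe group shrinks. With that gap in place of 33% vs 17%, the ICU shift for deaths on Days 1–6 is +1.4 h. The larger ICU and ventilation figures therefore need a real mortality difference inside those subsets.

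No calculation was run for antibiotic duration; the gap in its definition is the same.

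**The case against.** The strongest reply is that little hangs on this. No total is in the confirmatory hierarchy of SAP section 5.1.1, which uses the time-to-event counterparts with their death rule. Death is the worst category of the primary scale, all-cause mortality is a secondary endpoint, and mortality is tabulated by day. A reader of total ventilation time would have all of these alongside. This stands, and it limits the consequence to the interpretation of secondary estimates.

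A reader might infer that a mortality benefit will show up as harm. The documents do not support that. It requires the averted deaths to come earlier than typical survivor durations, with little shortening among survivors. Neither document gives death timing or survivor durations, and with later deaths every endpoint in the table favours the arm with fewer deaths. Nor is hospital stay much affected at the mortality the plan implies.

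A reader might also infer that the SAP abandons the Wilcoxon test. SAP section 1 says it is to be read together with the protocol, so leaving the test unnamed is a gap in alignment rather than a decision to drop it.

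Finally, replacing the totals with free days would change endpoints that the protocol defines. Among admitted or ventilated subjects it would still condition on an event that can occur after randomization. That also stands, and it argues for free days as a supportive analysis only.

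None of this supplies the missing rule. An estimate whose sign depends on when deaths occur, while survivor durations are identical, cannot be read as an effect on duration.

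**Conclusion.** The gap is in the text: four duration endpoints have no rule for death or withdrawal, and truncated values are compared as complete. Early deaths count in an arm's favour. How far this distorts the shift, and in which direction, depends on assumptions about subset mortality, survivor durations and death timing. Under the early-death scenario the distortion is material for ICU time (about +21 h) and ventilation time (about +39 h), given the assumed halving of mortality. It is small for hospital stay (about +1.5 h). With deaths spread to Day 28 the shift has the opposite sign.

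The supportable statement is that a mortality difference can distort, and with early deaths reverse, the estimated shift. A general claim that benefit would look like harm goes too far, and so does any claim that a confirmatory conclusion is at risk. The missing rule is certain; its size and direction are not. It should be corrected because the totals are named secondary endpoints with between-arm estimates and intervals, and they treat death in the opposite way to their paired endpoints.

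**What to change.** In SAP section 5.3.2.1 and the four definitions in section 5.3.1.1 (hospital stay, ICU, ventilation, antibiotics):

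- Extend the principle of section 5.3.1: give subjects who die a duration ranked longer than the longest observed one, and state the numeric value used for the Hodges-Lehmann shift.
- State a rule for subjects who withdraw while still hospitalized, in the ICU or ventilated, for example a sensitivity analysis that does not treat the truncated value as complete.
- Name the protocol's stratified Wilcoxon rank-sum test with the Hodges-Lehmann CI for all four durations.
- Show raw durations descriptively, separately for survivors and deaths.
- Optionally add days alive and free of hospital, ICU or ventilation to Day 28, with deaths scored 0 and the analysis population stated, as a supportive analysis beside the protocol's endpoints.

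The cost is SAP wording and derivation; no new data are needed. The downside is that the shift becomes a death-penalised composite and no longer reads as plain hours. Its size will also depend on the value assigned to deaths where mortality is high.

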ICU admission started post-baseline	
Incidence of post-baseline ICU admission
 
 - Admitted to ICU post-baseline - Not admitted to ICU post-baseline 
Note: In case a patient is in the ICU at baseline and (after discharge from the ICU) the patient is re-admitted post-baseline, this subject will be counted as "Admitted to ICU post-baseline".

First admission to intensive care unit (ICU)	
When was the subject first admitted to the ICU during the study?
 
Categories:
 
 - In ICU at baseline - Admitted in ICU Post-baseline - Never admitted to ICU
Time from ICU admission to ICU discharge (hours) [Time-to event]	
The time from max(first admission to ICU, first study drug intake) until the time of first discharge from the ICU.
 
Censoring and calculation of the time will be done analogous to "Time to hospital discharge".
 
Only subjects admitted to the ICU (at any point during the trial) are included in the analysis and analysis is restricted to the first ICU admission.

Time from ICU admission requiredness to ICU discharge readiness (days) [Time-to event]	
The date from max(requiring ICU level of care , first study drug intake) until the date of not requiring ICU anymore(= event), requiring ICU level of care to be defined by the investigator.
 
Censoring and calculation of the time (days) will be done analogous to "Time to hospital discharge"
 
Subjects that do not require ICU level of care will be excluded from this analysis and this analysis is restricted to the first required ICU level of care.

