Bootstrapping with replacement, considering also the actual proportion of subjects in each stratum, will be used to obtain a 100% sample size 10001 times. The median (95% CI) time-to event will be derived from the 10001 bootstrapped samples.

Cox Proportional Hazard model

A stratified Cox proportional hazards model will be used adjusted for the stratification factors and for the time from admission to start of treatment (for the time to hospital discharge and time to hospital discharge readiness),. The hazard ratio for the comparison of pimodivir versus placebo will be reported together with the 95% confidence interval. A Log-log plot of survival will be added to check the proportional hazard assumption of the Cox proportional hazards model.

For the subgroup analyses the Log-Log plot of survival will be shown for each subgroup category separately.

Logistic regression model

A logistic regression model (Firth's penalized likelihood approach), with treatment group and stratification factors as fixed effects, will be used to analyze binary outcomes and to obtain the odds ratios (95% CI) for the comparison of pimodivir versus placebo.

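### Logistic analyses of post-baseline ICU admission and ventilation starts keep subjects already in ICU or ventilated in the denominator, which dilutes the odds ratio for new episodes

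*SAP*

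**What the plan says.** SAP section 5.3.1.1 labels the first variable "Incidence of post-baseline ICU admission" and gives it two levels, admitted or "Not admitted to ICU post-baseline". A note deals with subjects already in ICU: "In case a patient is in the ICU at baseline and (after discharge from the ICU) the patient is re-admitted post-baseline", the subject is counted as admitted. The ventilation variable, which covers invasive and non-invasive support, is built the same way. A subject ventilated at baseline counts as started only if a second episode begins.

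Section 5.3.2.1 tabulates incidence parameters with this rule: "All Subjects in the applicable analysis set will be counted for the denominator of the proportion". It then sends the yes/no occurrence to the logistic regression of section 5.3.2, a Firth model that, "with treatment group and stratification factors as fixed effects, will be used to analyze binary outcomes". The stratification factors are NEWS2 category, type of standard of care, and time since symptom onset. ICU or ventilation status at baseline is not among them.

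Protocol section 4.1 admits both ICU patients (criterion 3) and invasively ventilated patients (criterion 5), so the affected group is expected to be present.

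Beside each two-level variable the SAP places a three-level one: present at baseline, first occurring after baseline, or never. These are tabulated but cannot enter a yes/no model as they stand.

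**The concern.** A subject in ICU at first dose cannot start a new ICU admission until the current one ends. Leaving such subjects in the denominator has two effects.

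- **Mixed code.** A subject who stays in ICU until death and one who leaves and recovers are both coded no. One who improves, leaves and relapses is coded yes. For this group the yes/no contrast does not order outcomes from good to bad.
- **Diluted and slightly drifting odds ratio.** Subjects who can contribute an event only by leaving and returning pull the two arms together. If treatment gets more of them out of ICU, more become able to return, which adds events to the treated arm.

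What is at stake is the interpretation of two supportive odds ratios that a reader of the study report would naturally take as the effect on needing ICU or ventilation for the first time.

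**Working it through.** **Scoring under the rule, for a subject in ICU at baseline**

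| Course | Code |
|---|---|
| Never leaves ICU, including until death | no |
| Leaves, does not return | no |
| Leaves and returns | yes |

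The first row is not written out in the SAP. It follows because the variable has only two levels and the note gives re-admission as the route to yes.

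**The plan's own figure.** None is given for these variables. The only computable design figure is the primary sample size (SAP section 1.4). The ordinal formula is N = 12(z₀.₉₇₅ + z₀.₉₀)² / [ln(OR)² (1 − Σp̄³)]. With OR 0.62 and the stated placebo distribution, N = 12 × 10.507 / (0.2285 × 0.9175) ≈ 602, against 600 stated. It reproduces. It matters here only as the source of 300 per arm.

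**Incidence under the rule.** Let b be the share in ICU at baseline, p the new-admission rate in the others, e the share of baseline-ICU subjects who leave, and r the share of those who return. Then

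I = (1 − b)p + b·e·r.

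The documents give none of b, p, e or r, so all values below are assumptions. Power is the two-proportion normal approximation at two-sided 5%, with 300 per arm as written and 300(1 − b) per arm when restricted. It ignores the Firth correction and the strata.

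**Dilution, assumption set 1:** p = 15% vs 8%, e = 60% in both arms, r = 15%. At b = 20%:

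- Placebo: 0.8 × 0.15 + 0.2 × 0.6 × 0.15 = 13.8%.
- Pimodivir: 0.8 × 0.08 + 0.2 × 0.6 × 0.15 = 8.2%.
- OR as written: (0.082/0.918) / (0.138/0.862) = 0.56.
- OR restricted: (0.08/0.92) / (0.15/0.85) = 0.49.

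**Dilution, assumption set 2:** p = 12% vs 6.4% (OR 0.50), e = 70% in both arms, r = 10%.

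| b | Set 1: OR as written (restricted 0.49) | Set 1: power, written vs restricted | Set 2: OR as written (restricted 0.50) | Set 2: power, written vs restricted |
|---|---|---|---|---|
| 5% | 0.51 | 73% vs 75% | 0.515 | 62% vs 64% |
| 10% | 0.52 | 69% vs 72% | 0.53 | 58% vs 62% |
| 20% | 0.56 | 59% vs 67% | 0.56 | 50% vs 57% |
| 30% | 0.595 | 49% vs 61% | 0.60 | 41% vs 51% |

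Dilution alone costs about 2 to 12 points. The restricted analysis has more power in every row despite fewer subjects.

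**Drift from faster ICU exit.** Suppose treatment has no effect on new admissions (12% in both arms), raises exit from 60% to 80%, and r = 10%. At b = 20%, I = 0.8 × 0.12 + 0.2 × 0.6 × 0.10 = 10.8% against 0.8 × 0.12 + 0.2 × 0.8 × 0.10 = 11.2%, so OR = 1.04. For b = 5%, 10% and 30% the OR is 1.01, 1.02 and 1.07. Meanwhile the subjects who never leave ICU, all coded no, number 300 × 0.2 × 0.4 = 24 on placebo and 300 × 0.2 × 0.2 = 12 on pimodivir at b = 20%.

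If the same exit benefit is added to set 1 at b = 20%, the pimodivir rate becomes 0.064 + 0.2 × 0.8 × 0.15 = 8.8%. The written OR moves from 0.56 to 0.60 and power from 59% to 49%.

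**The case against.** The strongest reply is that these variables carry little weight and the rest of the plan covers the problem cases.

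- **Status.** Neither variable is a protocol endpoint (protocol section 2.1.2) or one of the seven confirmatory endpoints (SAP section 5.1.1). No claim depends on them, and the plan sets no power target for them. This stands.
- **Other measures.** A reader might infer that the trial as a whole treats never leaving ICU as a good outcome, or that these are its main measures of progression. The documents do not support either reading. The hospital recovery scale scores ICU care, ventilation and death as its worst categories each day, and its primary model adjusts for baseline category. Time to clinical failure counts a recovery scale score above 3. Time to ICU discharge and time to end of ventilation treat a subject who dies first as censored at the longest observed time, so never leaving is the worst result there. This stands.
- **Tabulation.** The three-level variables already let a reader separate first admissions from baseline ICU stays. What is missing is the model on that set.
- **Legitimate question.** The proportion of all randomised subjects who need a new episode is a valid quantity and keeps randomisation intact. That is a fair reason to keep the all-subjects table. It does not make the odds ratio an effect on first admission or first ventilation.
- **Partial adjustment.** SAP section 7.6.1 imposes values on invasively ventilated subjects that score at least 3 + 2 + 3 = 8, which puts them in the upper NEWS2 stratum, a model term. This does not separate them from other subjects scoring 6 or more, and it does not cover ICU subjects who are not invasively ventilated.

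**Conclusion.** The point holds as a limited one. As written, the two logistic analyses mix subjects at risk of a first episode with subjects already in one, and for the latter the no code covers both the worst and the best course. The consequence is a diluted odds ratio for new ICU admission or ventilation, with a small adverse drift if treatment speeds ICU exit.

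The size cannot be derived from the documents. Over assumed baseline ICU shares of 5% to 30%, with equal ICU exit in the two arms, the power loss is about 2 to 12 points, and only 2 to 4 points at shares of 5% to 10%. The drift with no effect on new admissions is an OR of 1.01 to 1.07. A reader might infer from this that a real benefit would be hidden or reversed. The figures do not show that: with an assumed true OR near 0.5, the written OR stays between 0.51 and 0.60 under equal exit.

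A reader might also infer that death without ICU or ventilation must be counted as an event. That would change the estimand to a composite close to time to clinical failure. It is optional and not needed to cure the dilution. The primary analysis and the confirmatory sequence are unaffected.

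**What to change.** In SAP section 5.3.2.1, under incidence parameters:

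- Run the logistic regression for ICU admission started post-baseline in subjects not in ICU at baseline.
- Run the one for mechanical ventilation started post-baseline in subjects not mechanically ventilated (invasively or non-invasively) at baseline.
- Take both flags from the baseline characteristics in section 4.1, at status before first dose under the general rule of section 2.5. Do not use the baseline recovery scale category, which section 2.5 defines irrespective of when study drug started.
- Tabulate re-admission of baseline-ICU subjects and re-ventilation of baseline-ventilated subjects separately, by arm.
- Keep the all-subjects tabulation as descriptive.

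The flags precede treatment, so the randomised comparison is preserved within each restricted set. The cost is SAP wording, a population flag and a smaller denominator: for example 240 instead of 300 per arm if 20% are in ICU at baseline. No new data are needed.
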